3.2 Study Design

This study is designed as a multicenter, single-blinded, prospective, randomized, comparison IDE study between CellFX System and Electrodesiccation.

The Principal Investigator will select a sub investigator to be the blinded investigator to classify the healing characteristics and aesthetic appearance of each subject's selected lesions at baseline and treated lesions post treatment and at 7-days, 30-days, and 60-days following the last CellFX

treatment or Electrodesiccation. This sub investigator will be blinded to the treatment assignment. The subject may not be blinded to the treatment assignment.

Eligible subjects with a minimum of 4 and up to 10 SH lesions meeting the inclusion and exclusion criteria will be enrolled. The SH lesions may be present anywhere on the face except the scalp, nose and within the orbital region of the face. The subject must have at least two SH lesions on each side of the face. Subjects will be randomized to receiving the two treatments in a split-face design with CellFX being used on only one side of the face and Electrodesiccation on the other side. A minimum of two lesions must be treated with CellFX and a minimum of two lesions must be treated with Electrodesiccation per subject. Selected lesions for each treatment modality must be clearly separated in distance from each other so that lesion treatment and side effects can be assessed by the blinded site investigator.

All selected and qualifying study lesions will receive at least one CellFX or Electrodesiccation treatment. Each subject will be evaluated by the blinded site investigator at 7-days, 30-days, and 60-days post-initial CellFX and Electrodesiccation treatments. At the 30-day follow-up visit, if any lesion is rated 1-4 on the Global Aesthetic Improvement Scale (GAIS), the lesion must receive an additional treatment. In case of a second treatment, the subject will be evaluated by the blinded site investigator at 30-days and 60-days post-retreatment. Photography of the study lesions will be captured along with the blinded site investigator assessments at all visits.

Note:

Eligible lesions that should be treated and do not receive a retreatment will be considered a protocol deviation. The reason(s) for not receiving an additional treatment will be collected on the electronic case report form (eCRF). These subjects will remain in the study and will be included in the ITT population.

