4.4 Schedule of Events and Evaluations

Schedule of events and evaluations required for this study are provided in **Table 2**.

Table 2. Schedule of Events

Study Activity/ Procedure	Visit 1 Enrollment 1 st TX	Visit 2 7-days after 1 st TX	Visit 3 30-days after 1 st TX	Visit 4 60-days after 1 st TX	Visit 5* 90-days after 1 st TX
	Day -0	Visit Range ±3 days	Visit Range ±7 days	Visit Range ±7 days	Visit Range ±7 days
Informed Consent	✓				
Demographics, Medical HX, Fitzpatrick Skin Type	✓				
Randomization	✓				
1 st TX (CellFX + Electrodesiccation)	✓				
2 nd TX (CellFX and/or Electrodesiccation)			✓ If applicable		
Photographs of pre and post treated SH Lesions	✓	✓	✓	✓	✓
Wound Healing Characteristics	✓	✓	✓	✓	✓
Lesion Clearance Assessment			✓	✓	✓
Pain Score/Assessment for muscle twitching: Treated SH Lesions	✓		✓		
5 Point Investigator and Subject Global-Aesthetic Improvement Scale (GAIS)**			✓ ***	✓	✓
6 Point Subject Satisfaction Scale (SSS)/ 5 Point Recommendation Scale**				✓	✓
Adverse Event Assessment	✓	✓	✓	✓	✓
Study Exit				✓	✓

*The 90-day visit is only for subjects that received a second treatment at the 30-day visit.

** The three scales (GAIS, SSS, and 5-point recommendation scale) are completed one time by the subject (e.g., 60 days post last treatment).

***The GAIS is performed by the blinded site investigator at 30-days and 60-day post last treatment.

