4.5.3 CellFX Treatment / Electrodesiccation Treatment

- Up to 10 clinically diagnosed SH lesions that meet the study criteria will be selected by the treating investigator and prior to assigning lesions the subjects should have baseline photos taken.
- The site will log onto the Captivate EDC system. The randomization assignment will include the type of treatment and which side of the face for CellFX and Electrodesiccation.
- A template may be used to determine which treatment tip size will be used for each lesion – sizes range between 1.5 mm x 1.5 mm and 5.0 mm x 5.0 mm. The identified lesions will be numerically labeled.
- The blinded site investigator will then perform a baseline lesion(s) assessment.
- Photographic images of each selected lesion will be taken prior to using local anesthesia/numbing.
- Local anesthesia/numbing will be applied to all selected study lesions.
- Each lesion randomized to CellFX will be treated with pre-determined energy settings; each lesion randomized to Electrodesiccation will be treated as defined in **Section 3.5**.
- The subject will be asked to rate his/her pain immediately after each lesion treated with the CellFX and Electrodesiccation procedures by using a numerical rating score.
- The subjects will be asked whether they felt muscle twitching immediately after each lesion treated with CellFX.
- Post procedure lesion assessment will be performed by the blinded site investigator.
- Photographic images of each selected lesion will also be taken post-treatment.
- A light bandage and/or any physician recommended dressing may be applied before the subject leaves the clinic.
- Any adverse events will be identified and documented.

4.6. 7-Day Follow-up Visit

- Photographic images of each of the study lesions will be taken with pre and post lesion markings.
- All lesions will be clinically assessed by the blinded site investigator.
- Any adverse events will be identified and documented.

4.7 30-Day Follow-up Visit (Optional CellFX/Electrodesiccation Treatment #2)

- Photographic images of each of the study lesions will be taken with pre- and postlesion markings.
- All lesions will be clinically assessed by the blinded site investigator and rated using GAIS scale and the 4-point lesion clearance scale.
- If any lesion is rated 1-4 on the GAIS scale, a second treatment with CellFX or electrodesiccation will be performed to the previously treated lesion.

In case of a second CellFX or Electrodesiccation treatment:

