6.1.2 Primary Effectiveness Endpoint

The primary effectiveness endpoint is response measured by the Global Aesthetic Improvement Scale (GAIS) at 60 days following the last CellFX or Electrodesiccation treatment (60 days post-last treatment). GAIS score will be assessed by three independent observers, blinded to treatment assignment, who will classify the response for each lesion based on photographs taken at baseline and 60 days post last treatment. The 3 observers will assign a score based on the 5-level GAIS scale described in this section. For analysis purposes, the lesion will be classified as a responder if 2/3 blinded observers assign a score of 4 or 5, and as a non-responder if 2/3 blinded observers assign a score of 1, 2 or 3. The timing of the evaluation of this endpoint is lesion specific as some lesions may not require a second treatment with the CellFX System or Electrodesiccation. The GAIS scale²² describes aesthetic changes as follows:

GAIS Rating	Description
5=Much Improved	Marked improvement in appearance from the initial condition, touch-up treatment(s) is not indicated
4=Improved	Obvious improvement in appearance from the initial condition, but a touch-up or re-treatment is indicated
3=No Change	The appearance is essentially the same as the original condition
2=Worse	The appearance is worse than the original condition
1=Much Worse	The appearance is much worse than the original condition

The primary effectiveness endpoint is lesion-level GAIS response, defined as a score of 5 ("Much Improved") or 4 ("Improved") versus non-response defined as a score of 3, 2 or 1 ("No Change", "Worse", "Much Worse") for at least 2/3 blinded observers. This dichotomization of the GAIS scale has been used to define response in several previous cosmetic procedures.²³⁻²⁶

The 15% non-inferiority margin for the primary effectiveness endpoint is justified by consistency of treatment and ease of use with the CellFX system. Outcomes for standard of care Electrodesiccation procedures depend heavily upon operator skill and experience. Furthermore, electrodesiccation involves destruction of the entire gland but can lead to sequelae such as scarring and discoloration. Therefore, depending on the number of lesions and the cosmetic concerns of the patient, it may be necessary to avoid such interventions.²⁷ In contrast, the CellFX system is designed to be a straightforward procedure that is reproducible among providers with fewer sequelae.

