6.3 Sample Size Determination

Power for the co-primary endpoints was assessed using a bootstrap simulation. To accurately model within-subject correlation across lesions, the safety and efficacy outcomes for subjects with at least 4 lesions in a previous study (SH-009) were sampled with replacement. An assumed mapping was created between the clearance scale used in that study (**Section 6.7**) and the GAIS scale: lesions rated as “Clear” with hypopigmentation rated as “None” or “Mild” were classified as GAIS responders. Among lesions rated as “Mostly Clear” with hyperpigmentation rated as “None”, a binary random variable derived from a standard normal distribution was used to categorize 88% of these as GAIS responders with the remaining 12% categorized as non-responders. All other combinations of clearance and hypopigmentation were classified as non-responders. The resulting distribution of lesions had a GAIS response rate of 73%, which reflects discounts for both conversion to a different scale and a slight reduction in efficacy due to visibility differences in photo review compared to live assessment. Both primary safety outcomes (skin texture changes at 30 days post last treatment and pigment changes or scarring at 60 days post last treatment) were also calculated for each lesion.

For each simulation, subjects were selected from SH-009 with replacement. Half of the lesions for each selected subject were randomly assigned to each treatment, which assumes equal efficacy and safety across treatments. The GEE models for the primary safety and primary efficacy outcome were used as described in **Sections 6.1.1 and 6.1.2**. The proportion of simulations for which the 95% CI for the difference in proportions excluded the critical values for the hypotheses in **Sections 6.1.1 and 6.1.2** was calculated. This analysis (based on 10,000 simulations) demonstrated that 240 lesions (approximately 48 subjects) would provide at least 80% power for the coprimary endpoint hypothesis tests. To account for error in estimation of the mapping between lesion clearance and GAIS, a target of 260 lesions (approximately 52 subjects) with follow-up at 60 days after the last treatment was set for adequate power. Assuming 10% loss to follow-up, up to 60 subjects will be enrolled.

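### The Day 30 retreatment rule (GAIS 1-4) makes no provision for a lesion scored Clear, and the per-protocol definition uses a different trigger

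*Combined protocol and SAP*

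**What the plan says.** Section 3.2 sets the rule for the 30-day visit: "if any lesion is rated 1-4 on the Global Aesthetic Improvement Scale (GAIS), the lesion must receive an additional treatment". Its note adds that "Eligible lesions that should be treated and do not receive a retreatment will be considered a protocol deviation"; the reason for not retreating goes on the eCRF and the subject stays in the ITT population.

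Section 4.7 uses the same GAIS 1-4 trigger and says that "a second treatment with CellFX or electrodesiccation will be performed to the previously treated lesion". Its heading, however, reads "4.7 30-Day Follow-up Visit (Optional CellFX/Electrodesiccation Treatment #2", and Table 2 marks the second treatment "If applicable".

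Under Section 4.7 the blinded site investigator rates each lesion at that visit on both GAIS and the 4-point clearance scale (Clear, Mostly Clear, Partially Clear, Not Clear). The clearance score plays no part in the trigger.

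Section 6.1.2 defines the GAIS levels. Level 5 says a touch-up is not indicated and level 4 says one is. Levels 3, 2 and 1 only compare appearance with baseline; level 2, for example, reads "The appearance is worse than the original condition".

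Section 6.4 defines the per-protocol (PP) population by subject. Its retreatment condition is that treatment was repeated for lesions that were not clear at 30 days. It does not mention GAIS.

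**The concern.** GAIS levels 1 to 3 do not distinguish a site that still carries sebaceous hyperplasia from one where the lesion has gone but the skin has reacted. Read as written, Sections 3.2 and 4.7 require a second treatment in both cases, and withholding it is a deviation. The clearance score that could tell the two apart is recorded by the same rater at the same visit, but is not used.

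Three things are at stake:

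- **Exposure.** A second destructive treatment may be given to facial skin with no remaining lesion.
- **Safety co-primary endpoints.** Both are timed from each lesion's last treatment, so a skin reaction at Day 30 can change when, and after how much treatment, that lesion is assessed.
- **The PP set.** It applies a different retreatment criterion from the one sites must follow, so the same lesion can be handled inconsistently in conduct and in analysis.

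**Working it through.** There is no plan figure to reproduce. The check sets the passages side by side.

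**1. The two triggers.** The last two columns assume that the lesion was not retreated.

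| Day 30 ratings by the blinded investigator | Retreatment under 3.2 / 4.7 | Status under 3.2 | PP retreatment condition (6.4) |
|---|---|---|---|
| Clear, GAIS 5 | not required | no deviation | met |
| Clear, GAIS 4 | required | deviation | met |
| Clear, GAIS 1-3 | required | deviation | met |
| Not clear, GAIS 1-4 | required | deviation | not met |
| Not clear, GAIS 5 | not required | no deviation | uncertain |

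The conflict lies in rows 2 and 3. Section 6.4 does not say whether its criterion means the single category Not Clear or anything short of Clear, but a lesion scored Clear falls outside it on either reading. Row 5 is uncertain for that reason, and because the section's reference to repeating treatment as the protocol directs might be meant to import the Section 3.2 trigger.

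**2. Which GAIS levels leave the gap.** At level 4 the rater has, by choosing that level, said that retreatment is indicated, so rule and scale agree. At levels 1 to 3 the scale is silent and the rule alone compels treatment. The gap in the treatment rule therefore concerns Clear lesions rated 1-3. The conflict with the PP definition covers Clear lesions rated 1-4.

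The only place where the cause of a 1-4 rating matters is the footnote to Table 1, on mistargeted lesions. It affects the energy setting, not whether to retreat.

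**3. Effect on endpoint timing.** Section 6.1.1 times both safety co-primaries from each lesion's last treatment. With a second treatment at Day 30:

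- pigment change or scarring: 30 + 60 = Day 90, instead of Day 60;
- skin texture: 30 + 30 = Day 60, instead of Day 30.

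For a lesion treated once, the Day 30 texture finding is the co-primary observation. If that finding pulls GAIS below 5 and the lesion is retreated, the co-primary observation moves to Day 60.

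**4. Effect on the PP set.** Membership is decided by subject, so one lesion settles it for both sides of the face. At the planned 260 lesions in about 52 subjects, 260 / 52 = 5 lesions per subject. Each subject classified differently moves about 5 lesions, or 5 / 260 = 1.9% of the target.

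**5. Can the number of affected lesions be found?** No.

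- Section 1.5 reports hyperpigmentation of 45% and surface irregularities of 33% in SH-006. For SH-009 lesions treated once it reports 14%, 8% and 36%, and 2%, 1% and 10%, by energy level.
- It also says that the SH-009 surface irregularities resolved as tissue filled in where the lesion had cleared, so skin effects at cleared sites do occur.
- None of these rates is cross-tabulated with clearance or GAIS at Day 30.
- The 73% response rate in Section 6.3 leaves 1 - 0.73 = 27% simulated non-responders, about 0.27 x 260 = 70 lesions. The Clear share of these is not given, and the mapping does not separate GAIS 4 from 5. It gives no Day 30 retreatment rate.

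**The case against.** The best defence is that the rule is deliberate. Section 6.4 states the intent of up to two sessions of each treatment. The same trigger applies to both sides of each face and is scored blind, so the co-primaries compare two strategies that include retreatment. That stands: nothing here shows bias between arms. It does not supply the missing provision for Clear lesions or remove the conflict with the PP definition.

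It is also fair that GAIS carries a retreatment judgement where levels 4 and 5 meet. This narrows the gap in the treatment rule to levels 1-3.

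Much of the needed data is already planned: Day 30 clearance, wound-healing components by lesion, reasons for not retreating, and a subgroup on secondary treatments (Section 6.5). A new eCRF item would therefore add little.

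A reader might infer two stronger points that the documents do not support:

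- **That Sections 3.2 and 4.7 give opposing rules, so sites will diverge.** The word Optional stands only in the 4.7 heading. The instruction beneath it is mandatory on the same trigger, and Table 2 can be read as meaning conditional. These are minor wording mismatches, and divergent site practice would be conjecture.
- **That the plan itself rates cleared but discoloured lesions as GAIS 1-3.** Section 6.3 does say "All other combinations of clearance and hypopigmentation were classified as non-responders", which takes in Clear lesions with more than mild hypopigmentation. But that mapping is an assumption for converting SH-009 data in the power simulation. It does not instruct the Day 30 rater. It concerns only hypopigmentation above mild for Clear lesions, and a non-responder may simply show no change. The responder definition it relies on belongs to three photo observers at 60 days after last treatment.

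**Conclusion.** The point holds in limited form. Retreatment is mandatory for GAIS 1-4 at Day 30, no provision covers a lesion scored Clear, and Section 6.4 applies a different criterion that diverges on exactly those lesions. This follows from the text alone. It assumes only that a site can be scored Clear and still be rated below 5, which the scales allow.

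The size is unknown. A reader might multiply the earlier pigment rates by a guessed clearance rate to get a count of needless retreatments. Such a count would only be a product of assumptions, since the rates cited are mainly for hyperpigmentation, mostly mild, and not tied to Day 30 GAIS. What can be stated is the effect per case: one further treatment, a 30-day shift in both safety co-primary assessments of that lesion, and, through subject-level PP membership, about 5 lesions counted in or out.

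This is a matter of exposure, endpoint timing and consistent classification. It does not undermine the randomised comparison.

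**What to change.** The sponsor should reconcile Section 3.2 (rule and deviation note), Section 4.7 (heading and text), Table 2 and Section 6.4 into one retreatment trigger, used identically for treatment, deviations and PP membership. The text should state what applies when the Day 30 clearance score is Clear and GAIS is 1-4. If Section 6.4 keeps a clearance criterion, it should say which clearance scores count as not clear. Which clinical rule is right is for the sponsor's clinical team; this review does not propose one.

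In the analysis plan, add a table of retreated lesions by arm, cross-tabulated with the Day 30 clearance score, to be read beside the safety co-primaries. The data are already collected.

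The cost is a protocol wording change, brief site retraining and one extra table. No visits, subjects or eCRF items are added.

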3.3 Randomization

All enrolled subjects will be randomized to receive the two treatments in a split-face design with CellFX being used on only one side of the face and Electrodesiccation on the other side. Randomization will be implemented through the Electronic Data Capture (EDC) system. The randomization assignment will include the type of treatment and which side of the face to treat first. For example: 1) First Treatment = CellFX and 2) Side of Face = Right. All randomized subjects will be included in the intent-to-treat analysis.

3.4 CellFX Procedure

The intended CellFX treatment device is described as the CellFX® System using the skin contacting component referred to as the “tip” ranging in sizes from 1.5 mm x 1.5 mm to 5.0 mm x 5.0 mm in length and width and 2.0 mm in depth. Each tip will be used with pre-determined energy settings displayed on the CellFX Console and are provided in **Table 1**. These energy settings do not exceed the maximum safe ranges of settings previously tested in clinical studies. A local anesthetic will be used to manage potential treatment discomfort during the CellFX treatment. All subjects will be monitored for muscle “twitching” on the face during each CellFX treatment and the subjects will be asked whether they felt any muscle “twitch” during the treatment.

Table 1: Energy Settings per Tip Size and Fitzpatrick Skin Type

Tip Size (L x W, mm)	Fitzpatrick Skin Type	1 st Treatment Level mJ/mm ³	Re-Treatment Level mJ/mm ³ *
1.5 x 1.5	I-II	190	150
1.5 x 1.5	III	150	150
2.5 x 2.5	I-II	60	30
2.5 x 2.5	III	30	30
5.0 x 5.0	I-II	45	30
5.0 x 5.0	III	30	30

**If a lesion was rated as 1-4 on the GAIS scale at the 30-day follow-up visit due to a mistargeted lesion that was confirmed by a photograph taken immediately post CellFX procedure, it is recommended to use the first treatment level energy settings.*

3.5 Standard Electrodesiccation Procedure

Electrodesiccation will be standardized across all investigational sites. Investigators will perform the Electrodesiccation procedure with a Segal® Hyfrecator Needle and will use the same local anesthetic to numb the skin. Laser or curettage post Electrodesiccation will be prohibited. Pulse Biosciences will provide a training video on how to perform the Electrodesiccation procedure to the treating site investigators.

3.6 Site Selection

The study will be conducted at up to 5 clinical research sites. The sites will be selected based on the appropriate patient population, board certified dermatologist, and sufficient resources to support this IDE study.

3.7 Number of Subjects

Up to 60 subjects at up to 5 sites will be enrolled.

3.8 Clinical Study Duration

It is anticipated that the enrollment of subjects in this study will take approximately 2-3 months in duration. All subjects included in this clinical investigation will return for follow-up visits at 7-days, 30-days, and 60-days, post first CellFX or Electrodesiccation treatment. For subjects who received a second CellFX or Electrodesiccation treatment, at the 30-day follow up visit, will return for one additional follow-up visit at 90-days from their initial treatment date. The total study duration will be 6 months.

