6.1.1 Primary Safety Endpoints

The first primary safety endpoint is the presence or absence of hyperpigmentation, hypopigmentation or scarring at 60 days from the last CellFX or Electrodesiccation treatment as assessed by the blinded site investigator. The timing of the evaluation of this endpoint is lesion specific as some lesions may not require a second treatment with the CellFX System or Electrodesiccation. Lesions will be categorized as having this safety event if any component (hyperpigmentation, hypopigmentation, or scarring) is present at the follow-up visit 60 days after the last treatment.

Clinical justifications for the 15% non-inferiority margin for the primary safety endpoints include the avoidance of electrosurgical smoke plume, which may be harmful to patients and providers,²⁰ as well as existing safety data that demonstrate no serious adverse events. Safety data show a comparable safety profile for CellFX compared to the predicate devices for this indication, with the suggestion of faster healing.

The statistical hypotheses to be evaluated for the pigmentation and scarring primary safety endpoints are:

$$\begin{aligned} H_0: p_{CellFX} - p_{Electro} &\geq 15\% \text{ at 60 days post last treatment, versus} \\ H_A: p_{CellFX} - p_{Electro} &< 15\% \text{ at 60 days post-last treatment} \end{aligned}$$

Where p_{CellFX} and $p_{Electro}$ are the proportion of lesions with any of these events (hyperpigmentation, hypopigmentation, or scarring) in each treatment group. The null hypothesis will be rejected if the upper bound of the 2-sided 95% confidence interval for the absolute difference in proportions ($p_{CellFX} - p_{Electro}$) is less than 15%. This approach is equivalent to a 1-sided test with a 2.5% type I error rate. To be clinically meaningful, the absolute difference should not exceed 7.5%.

This second safety endpoint is the presence or absence of skin textural changes (scaling, flaking etc.) at 30 days from the last CellFX or electrodesiccation treatment as assessed by the blinded site investigator. The timing of the evaluation of this endpoint is lesion specific as some lesions

may not require a second treatment with the CellFX System or electrodesiccation. Lesions will be categorized as having this safety event if any skin textural change is present at the follow-up visit 30 days after the last treatment.

The statistical hypotheses to be evaluated for the skin texture change primary safety endpoint are:

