9.0 ADVERSE EVENTS

Pulse Biosciences will classify each reported Adverse Event according to ISO 14155:2011. All protocol specific AEs, whether device-related or not, will be recorded on the AE case report form and reported. Data to be collected will include the description of the AE, onset, and resolution dates (or whether the AE is ongoing), severity, management/treatment, outcome, and determination of the relationship to the device and/or procedure. All AEs related to the lesion site(s) should be reported and classified by the blinded site Investigator and to be followed by the treating Investigator to determine the relationship of the AE to the device or the study procedure.

All AE information will be collected from enrollment through 60 days following the last CellFX and Electrodesiccation procedures. All AEs will be followed until the event has resolved (in the case of permanent impairment, the event will be followed until it stabilizes, and the overall clinical outcome has been ascertained).

When reporting AEs/SAEs, the Investigator should include the following information:

- Description of event
- Onset of event
- Duration of event
- Severity
- Relationship to device or procedure
- Action taken
- Subject outcome

Severity describes the intensity of an event and will be assessed as:

- **Mild:** The AE does not interfere in a significant manner with the subject's normal functioning level.
- **Moderate:** The AE produces some impairment of function but not hazardous to health.
- **Severe:** The AE produces significant impairment of function or incapacities and/or it is a hazard to the subject.

Relationship to device or procedure will be assessed as:

- **Unlikely:** There is no indication that the AE was caused by the investigational or standard of care device.
- **Possibly:** It cannot be excluded that the AE was caused by the investigational or standard of care device.
- **Likely:** A causal relationship between the investigational or standard of care device and the AE is at least a reasonable possibility; i.e. there is evidence or argument suggesting a causal relationship.

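### Visits 4 and 5 are dated from the first treatment while the co-primaries run from the last, so retreated lesions may be assessed at 16–44 and 46–74 days

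*Combined protocol and SAP*

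**What the plan says.** Two anchors are in use.

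**First treatment.** Section 3.8 dates the 7-, 30- and 60-day visits from the first treatment and adds, for retreated subjects, that they "will return for one additional follow-up visit at 90-days from their initial treatment date". The column heads of Table 2 (Section 4.4) agree: "Visit 3 30-days after 1 st TX", "Visit 4 60-days after 1 st TX" and, for Visit 5, "90-days after 1 st TX". Each of these three visits has a ±7-day range. Retreatment is tied to Visit 3: "The 90-day visit is only for subjects that received a second treatment at the 30-day visit".

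**Last treatment.** Section 3.2 says that after a second treatment "the subject will be evaluated by the blinded site investigator at 30-days and 60-days post-retreatment", without a window. The third footnote to Table 2 places the blinded site investigator's GAIS 30 and 60 days after the last treatment. Section 6.1.1 sets pigmentary change or scarring at 60 days after the last treatment, and counts a texture event "if any skin textural change is present at the follow-up visit 30 days after the last treatment". Section 6.1.2 takes GAIS response from photographs 60 days after the last treatment. Sections 6.1.1 and 6.1.2 both make the timing specific to the lesion.

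The text does not say which anchor governs visit dates, gives no rule for re-dating Visits 4 and 5 to the actual retreatment date, and sets no analysis window around 30 or 60 days after the last treatment.

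**The concern.** A lesion treated once contributes its texture result at Visit 3 and its pigment, scarring and GAIS results at Visit 4. A retreated lesion contributes the same results at Visits 4 and 5. For the first kind, the interval since treatment varies only with the date of the visit itself. For the second kind it varies with two dates, that of Visit 3 and that of the later visit, because the later visit is not tied to the day of retreatment.

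The endpoints are presence or absence of skin changes on a given day, and Section 1.5 describes the pigment and surface changes seen in SH-009 as transient. Looser timing therefore adds noise to the co-primary outcomes of retreated lesions. It is most noticeable for texture, where the earliest permitted assessment, 16 days, is about half the intended 30.

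Retreatment may not be rare. SH-009 reported 12% to 27% (Section 1.5). Here every lesion rated GAIS 1 to 4 must be retreated (Section 3.2), which includes lesions rated Improved; the rate expected under that trigger is not given.

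**Working it through.** **Inputs** (Table 2): Visit 3 at 30 ±7 days, Visit 4 at 60 ±7, Visit 5 at 90 ±7, all from first treatment. Retreatment is at Visit 3.

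**The plan's own nominal timing.** 60 − 30 = 30 days and 90 − 30 = 60 days. The target days give the intended intervals exactly.

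**Permitted days.** Visit 3: Day 23–37. Visit 4: Day 53–67. Visit 5: Day 83–97.

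**Interval since retreatment.** The minimum is the earliest later visit minus the latest Visit 3. The maximum is the latest later visit minus the earliest Visit 3.

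- Visit 4: 53 − 37 = 16 to 67 − 23 = 44 days.
- Visit 5: 83 − 37 = 46 to 97 − 23 = 74 days.

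**By day of retreatment:**

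| Visit 3 on | Interval at Visit 4 | Interval at Visit 5 |
|---|---|---|
| Day 23 | 30–44 | 60–74 |
| Day 30 | 23–37 | 53–67 |
| Day 37 | 16–30 | 46–60 |
| Lesion treated once | 23–37 (at Visit 3) | 53–67 (at Visit 4) |

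Each row is 14 days wide. For a given lesion the window is shifted by up to 7 days, in either direction, according to its Visit 3 date. Pooled over all Visit 3 dates the envelope is ±14 days.

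**How often it would matter (assumption).** The plan gives no distribution of visit dates. Suppose the deviations *a* (Visit 3) and *b* (later visit) are independent and uniform on −7, …, 7, giving 15 × 15 = 225 pairs.

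- The error in the interval is *b* − *a*, with mean zero.
- Pairs with |*b* − *a*| > 7: 2 × (7 + 6 + 5 + 4 + 3 + 2 + 1) = 56, and 56/225 = 25%.
- The 16-day extreme is one pair: 1/225 = 0.4%.
- The variance of one deviation is (15² − 1)/12 = 18.7, so the SD is 4.3 days for a lesion treated once. The difference of two has variance 37.3, SD 6.1 days.

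At the SH-009 retreatment rates, read as proportions of lesions, 0.12 × 0.25 = 3% to 0.27 × 0.25 = 7% of all lesions would be assessed more than 7 days off target.

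**After re-anchoring.** With Visits 4 and 5 at 30 ±7 and 60 ±7 days from retreatment on Day *r*, the intervals become 23–37 and 53–67, as for a lesion treated once. Visit 4 must also serve once-treated lesions in the same subject (Day 53–67), so it must lie in the overlap of [*r* + 23, *r* + 37] with [53, 67]:

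- *r* = 23: Day 53–60.
- *r* = 30: Day 53–67.
- *r* = 37: Day 60–67.

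The overlap spans 7 to 14 days and is never empty.

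**The case against.** The strongest reply is that the schedule is centred correctly. Target days give exactly 30 and 60 days, the drift is symmetric, and the extreme intervals need both visits at opposite window edges. That stands, and it limits the point to added spread.

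Second, Section 3.2 and the Table 2 footnote already refer to the last treatment, so the plan does not endorse a 16-day texture assessment. This also stands in part: it is a conflict of wording. But the only visit windows in the text are those counted from the first treatment, and a site working from Table 2 would be within them. Section 6.0 refers to an SAP for further detail, and no separate SAP text is in the document reviewed, so an analysis window set there cannot be ruled out. Such a window could accept or set aside an early observation; it could not move it to Day 30.

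Four stronger readings are tempting and not supported:

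- *Every retreated lesion has a ±14-day window.* It does not. ±14 is the pooled envelope; a lesion retreated on Day 30 has the same windows as a lesion treated once.
- *Timing is confounded with treatment, so the comparison is biased.* Both sides of the face share visit dates. If retreatment rates differ, the treatments differ in the spread of timing, not in its mean. A directional effect would also need visit dates to drift systematically or a strongly non-linear course of resolution, and the documents show neither.
- *Section 1.3 shows that healing is too slow for the early assessments.* Its sentence on healing taking some weeks concerns curettage combined with electrosurgery, and Section 3.5 prohibits curettage after electrodesiccation here. Section 1.5 calls the skin changes transient but gives no time course.
- *First-treatment dating is what cuts safety follow-up short.* Section 9.0 says "All AE information will be collected from enrollment through 60 days following the last CellFX and Electrodesiccation procedures". A subject retreated on Day 37 and seen on Day 83 would indeed exit at 46 days, but a subject treated once may exit on Day 53. The mismatch between a −7-day exit window and a 60-day AE period affects all subjects and should be reconciled separately.

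**Conclusion.** The point holds as a scheduling inconsistency that is worth correcting. The visit windows permit co-primary assessments of retreated lesions at 16–44 and 46–74 days, where lesions treated once are held to 23–37 and 53–67. These limits follow from Table 2 without assumptions. The 25% figure rests on independent, uniform visit days: it would be lower if visits cluster near target or if subjects late for Visit 3 also tend to be late afterwards, and higher if early and late visits tend to alternate. The share of all lesions affected depends on a retreatment rate that the plan does not give for its GAIS trigger.

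The consequence is extra noise in the timing of the co-primaries, greatest in relative terms for 30-day texture. It would differ between treatments only in spread, and only if their retreatment rates differ. Nothing here shows a bias in the non-inferiority comparisons.

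**What to change.** Reconcile Section 3.8 and Table 2 with Section 3.2. For any subject retreated at Visit 3, schedule Visit 4 at 30 ±7 days and Visit 5 at 60 ±7 days from the actual retreatment date. Take Visit 4 within the overlap with Day 53–67, so that once-treated lesions in the same subject stay in their own window: Day 53–60 after retreatment on Day 23, Day 60–67 after retreatment on Day 37. Subjects with no retreatment keep the present schedule.

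The change needs revised wording in two places and a visit-date calculation in the EDC system. It adds no visit and alters no treatment rule. The main cost is a Visit 4 window of 7 to 14 days for retreated subjects, which may produce some missed or out-of-window visits; Section 6.6 already names missed visits as the likely source of missing data. The latest possible Visit 5 also moves from Day 97 to 37 + 67 = Day 104.
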